4.5.2 Study Day and Study Reference Period

For events that occurred after the implantation of the Scaffold:

Study Day = visit date – date of surgery + 1

For events occurred before implantation of the Scaffold:

Study Day = visit date – date of surgery

4.5.3 **Baseline and Change from Baseline**

Time points that can be used as a “baseline” for assessments are primarily the assessment, immediately prior to the open spine surgery, but also may include at screening or at hospital discharge as denoted in their respective analysis.

Unless indicated otherwise change from baseline (CFB) will be calculated as follows:

- CFB = Value at Visit - Baseline

5. STATISTICAL ANALYSIS GENERAL CONSIDERATIONS

The results will be presented primarily via data tabulation by subject ID and time course because this is an early feasibility study with a small sample size. Group descriptive statistics and cumulative statistics will be presented, as appropriate.

5.1 Analysis Populations

The following analysis populations will be prepared for this study:

Screened Set:

The screened population will include all subjects who signed the informed consent form and were screened for participation in this study. This population will be used when describing disposition throughout the study.

Safety Set:

The Safety Set includes all enrolled subjects (i.e. subjects who have signed an Informed Consent Form) that passed the screening assessments. The Safety Set will serve as the analysis set for listings, where data will be presented stratified by screen failures and non-screen failures (as designated by the subject status eCRF page, determined by eligibility procedures at the Screening visit and surgery).

Safety Set Excluding Screen Failure Subjects:

A subgroup of the Safety Set, "Safety Set Excluding Screen Failures" will be considered the subjects in the safety set, but excluding subjects identified as screen failures on the subject status eCRF page. This set will be used for safety table summaries.

All Treated Analysis Set:

The All Treated Analysis Set includes all subjects who have a successful Scaffold implant. The All Treated Analysis Set will serve as the analysis set for all efficacy endpoints.

Primary Endpoint Analysis Set:

The Primary Endpoint Analysis Set includes all subjects who have a successful Scaffold implant, no major protocol deviations that affect data quality, and who have completed the 6-month Primary Endpoint Follow-up Visit. The Primary Endpoint Analysis Set will serve as the analysis set for the primary efficacy endpoint.

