6.1 Study Subjects

6.1.1 Subject Disposition

The summary tables will provide frequency counts for subject disposition (all enrolled [Safety Set], screen failures, Unsuccessful Scaffold Implantation [with and without durotomy performed], subjects with successful implantation of the Scaffold [All Treated Set], subjects who completed the 12-month post-implantation visit, subjects who completed the 24-month post-implantation visit, subject in the Primary Endpoint Analysis Set, and subjects who withdrew early from the study and reason for discontinuation).

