6.3 Safety Analysis

Safety analysis will be performed using all subjects in the Safety Population Excluding Screen Failure Subjects. The safety data will be presented descriptively and no formal statistical analyses are planned. The following sections provide the safety presentations for the Safety Set Excluding Screen Failure Subjects.

The primary safety analysis of the study will be presented upon completion of the 6 Month Primary Endpoint Follow-up Visit (6 Months post-Scaffold) for the subjects in the Safety Set Excluding Screen Failures.

Additional safety Analysis may be performed for information obtained after the 6 Month Primary Endpoint Follow-up Visit (12 month and 24 month post-Scaffold follow-up visits) upon the completion of collection of clinical data, as needed.

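### The Safety Set definition contradicts itself, and a screen-failure label set at surgery can decide whether an operated subject appears in the safety tables

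*SAP*

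**What the plan says.** SAP Section 5.1 opens with: "The Safety Set includes all enrolled subjects (i.e. subjects who have signed an Informed Consent Form) that passed the screening assessments". It then makes this the set for listings, "where data will be presented stratified by screen failures and non-screen failures". The status comes from the subject status eCRF page and is "determined by eligibility procedures at the Screening visit and surgery". A subgroup is formed from the Safety Set, "but excluding subjects identified as screen failures on the subject status eCRF page", and the section adds: "This set will be used for safety table summaries". Section 6.3 repeats the rule: "Safety analysis will be performed using all subjects in the Safety Population Excluding Screen Failure Subjects".

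Three other places bear on the point:

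- Section 6.1.1 uses Safety Set as the label for all enrolled subjects. It lists screen failures as one disposition category and, as a separate one, "Unsuccessful Scaffold Implantation [with and without durotomy performed".
- Section 6.3.2 gives successfully implanted subjects their own tabulation within each safety-event table.
- The All Treated Analysis Set in Section 5.1 holds successful implants only.

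**The concern.** There are two linked problems. First, the Safety Set cannot be programmed as written. Subjects who passed screening cannot include subjects who failed at the Screening visit, yet the set is to be split on that status.

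Second, entry to the safety tables follows an eCRF label and not exposure to surgery. The label may be assigned as late as surgery, and the SAP does not say which label applies to a subject whose eligibility fails after the operation has started. Section 6.1.1 shows that an attempt can end without a Scaffold, in some cases after durotomy. Section 4.4 makes cerebrospinal fluid leakage, surgical injury to the cord and wound infection safety endpoints, and Section 6.3.2 counts as device effects those events at least possibly related to the implant procedure. In a study this small, whether one operated subject is tabulated can decide whether a rare harm appears in the tables at all.

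**Working it through.** The plan gives no figure to reproduce here. The check compares the definitions and counts the planned outputs.

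**1. Is the Safety Set consistent?** Three statements do not fit together.

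- Section 5.1 limits it to those "that passed the screening assessments".
- Section 5.1 also splits it by screen failure, with status decided at the Screening visit as well as at surgery.
- Section 6.1.1 treats it as all enrolled.

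Reading screen failure as a surgery-stage event only would remove the clash. But Section 5.1 names the Screening visit, and Section 6.1.1 says all enrolled. On that reading, moreover, every excluded subject would have reached the surgery stage. Separately, Table 14.1.1.2 reports reasons for screen failure on the set that excludes screen failures, so it is empty by definition.

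**2. Follow one subject.** Take a subject who consented, passed screening, had an incision, was then found ineligible and received no Scaffold. The SAP does not say which row applies.

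| Status recorded | Safety Set Excluding Screen Failures | All Treated Set |
|---|---|---|
| Unsuccessful implantation | in | out |
| Screen failure | out | out |

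**3. Count the planned safety tables (Section 9.1).**

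- 14.3.1: 1 + 1 + 15 = 17
- 14.3.2: 1 + 6 = 7
- 14.3.4: 8
- 14.3.5: 4
- 14.3.6: 3
- 14.3.7: 1

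The total is 17 + 7 + 8 + 4 + 3 + 1 = 40. Tables 14.3.1.2 and 14.3.2.1 use the All Treated Set; the other 38 use the set without screen failures. None uses the full Safety Set. For safety events alone (14.3.1 and 14.3.2) the split is 22 and 2 of 24. A subject in the second row above is therefore in 0 of 40 tables; one in the first row is in the population of 38.

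**4. Check the listings.** Listings 16.2.7.1 and 16.2.7.2 (safety events, serious safety events) use the full Safety Set, so the events remain visible there. Listings 16.2.5.1 (surgery), 16.2.5.3 (investigational product events), 16.2.5.4 (hospital discharge), 16.2.12 (ultrasound) and 16.2.13.1 (evoked potentials) exclude screen failures, and no screen-failure counterpart is listed. Section 6 says that listings cover all subjects and visits.

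**5. Possible size (illustration only).** The SAP gives no count of subjects flagged at surgery and no size for the safety-table set. Assume 16 retained subjects, the Primary Endpoint Analysis Set count in Section 3.2.1, taken as a floor, and 1 to 3 dropped subjects. Rates are x/n with exact (Clopper-Pearson) 95% intervals.

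| Assumed events | Dropped subjects left out | Dropped subjects kept |
|---|---|---|
| One event, in the only dropped subject | 0/16 = 0% (0 to 20.6%) | 1/17 = 5.9% (0.1 to 28.7%) |
| One event, in one of three dropped | 0/16 = 0% (0 to 20.6%) | 1/19 = 5.3% (0.1 to 26.0%) |
| Events in all three dropped | 0/16 = 0% (0 to 20.6%) | 3/19 = 15.8% (3.4 to 39.6%) |
| One event in a retained subject, none in three dropped | 1/16 = 6.3% (0.2 to 30.2%) | 1/19 = 5.3% (0.1 to 26.0%) |

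The reported rate can move either way.

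**The case against.** The strongest reply is that the SAP appears designed to keep these subjects. Section 6.1.1 lists unsuccessful implantation, with and without durotomy, apart from screen failures. Section 6.3.2 shows implanted subjects separately within the safety tables, which makes sense only if those tables also hold non-implanted subjects. Failure at surgery may also be found before any incision: Table 1 requires a confirmatory ISNCSCI examination within 8 hours before surgery, and Listing 16.2.1.2 is titled as pre-operative eligibility. The rules for the status page may be in the protocol or eCRF, which are not at hand. Safety is descriptive, and the event listings keep the full Safety Set.

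Most of this stands, and it rules out several stronger readings. A reader might infer that subjects opened but not implanted are dropped from the safety tables; the SAP does not say so, and Sections 6.1.1 and 6.3.2 point the other way. A reader might infer that their harms vanish from the report; the event listings would show them. A reader might infer that procedural harm is understated; the last row of the illustration shows that restoring event-free subjects lowers a rate. Nor does 16 measure the safety denominator, since the Primary Endpoint Analysis Set also requires a 6-month visit and no major data deviation.

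What the reply does not supply is a rule. The exclusion in Section 5.1 depends on the flag alone, whatever the stage at which it was set, and nothing in the SAP makes the two labels mutually exclusive or ties either of them to incision.

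**Conclusion.** The concern holds in a limited form. The Safety Set is contradictory as written, and Table 14.1.1.2 cannot contain data on its stated population. The safety-table set excludes by a label that can be assigned at surgery, with no rule in the SAP against giving it to a subject whose operation has begun. A subject so labelled would be absent from all 40 planned 14.3.x tables and from several surgical listings, while the subject's events would remain in Listings 16.2.7.1 and 16.2.7.2.

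Whether any subject is affected is unknown, as is the direction of any change in rates. The conclusion rests on the SAP text alone; an explicit status rule in the protocol or eCRF instructions could narrow it, but would not cure the wording of Section 5.1. It should be corrected because the safety tables ought not to depend on how a late eligibility failure happens to be coded.

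**What to change.** - Define the Safety Set once in Section 5.1 and use the same meaning in Section 6.1.1: drop either the restriction to subjects who passed screening or the stratification by screen failure.
- Base the safety tables on all consented subjects in whom surgery with intent to implant was started, taken as incision made, whatever their eCRF screen-failure flag.
- State that screen failure and unsuccessful implantation are mutually exclusive, with screen failure reserved for exclusion before incision.
- Keep the separate implanted tabulation already planned in Section 6.3.2, and add not-implanted columns with and without durotomy, so that the added subjects do not dilute device rates.
- Move Table 14.1.1.2 to the Screened Set.
- Apply the same set to the surgical-detail listings named above.

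The cost is SAP wording, a few more table columns and a possibly changed denominator. No new safety-event data are needed, because events are already to be listed for the full Safety Set. If no operated subject carries the flag, the numbers stay as they are and only the ambiguity goes.

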5.2 Test Hypothesis and *P*-Value Justification

No formal statistical hypothesis was used to determine the sample size. No formal statistical tests are planned for the study.

5.3 Procedures for Handling Missing Data and Outliers

Unless indicated otherwise, no imputation will be done for missing data. However, missing adverse event start dates or partial start dates that result in the assessment of the event beginning before or after the implantation will result in the event being considered as having started after the initiation of device implantation.

Safety events with missing intensity assessments will be tabulated as “Severe” and safety events with missing relationship causality will be tabulated as “Definitely Related” for the purpose of analysis (with a footnote stating it was derived as such); and the missing data will be presented in the data listing as is.

The clinical database will be locked after all subjects complete their 6-month Primary Endpoint Follow-up Visits for the Primary Endpoint Analysis and writing of the Clinical Study Report is completed.

5.4 Interim Evaluations and Primary Analysis

One interim evaluation was performed at the time the first 5 subjects received the Scaffold implant and completed the 6-month post-Scaffold implantation Follow-up Visit. The purpose of the interim evaluation was to support conversion of the pilot study into an HDE probable benefit study enrolling up to 36 subjects to achieve 20 subjects in the Primary Endpoint Analysis Set.

Subjects who received the Scaffold are to be followed for 24-months in clinic, and then the subjects will be followed annually by telephone contact for an additional 8 years. At the time of the last subject in the Primary Endpoint Analysis set completes the 6 Month Post-Implantation Visit, the Primary Analysis of all available data will be presented in tables, listings, and figures and a Clinical Study Report will be prepared. Data collected during the Long-term Follow-up will be reported via the format of Investigation Device Exemption (IDE) annual update.

A Data Safety Monitoring Board (DSMB) will be formed to evaluate safety and efficacy on an on-going basis. The DSMB will be notified of all serious safety events, safety events of interest, and study stopping rules. The DSMB may recommend that the study enrollment be put on hold or the study be terminated should safety events occur that are Scaffold-related and distinct from a safety event that may be associated with standard of care open spine surgery or sequelae considered part of the normal course of a non-penetrating SCI (contusion injury) following such surgery.

Additional safety reviews or ad-hoc analyses may be scheduled as recommended by the DSMB or the sponsor.

6. STATISTICAL ANALYSIS METHODOLOGY

All data collected for this study will be presented in summary tables, listings, and figures (TLFs) as indicated in Appendix 1 of this SAP. Shells for TLFs with enough detail for programming will be provided as a guide to develop the programming SAS codes. These shells will be in sufficient detail to simulate the actual TLFs when they are created from the locked database.

The results will be presented primarily via data tabulation and listed by subject ID and time course because this is an HDE Probable Benefit study with a small sample size. Group descriptive statistics and cumulative statistics will be utilized if appropriate.

Tabulations for continuous data will use a standard set of summary statistics: number of observations available (n), mean, standard deviation (SD), median, and range (minimum, maximum).

Categorical or dichotomous data will be tabulated using counts and percentages. The numerator and denominator for each percentage calculation will be specified in the footnotes of table shells.

Data listings will present all information recorded in eCRFs and any derived variable(s) included in the analysis datasets for all subjects and visits.

6.1 Study Subjects

6.1.1 Subject Disposition

The summary tables will provide frequency counts for subject disposition (all enrolled [Safety Set], screen failures, Unsuccessful Scaffold Implantation [with and without durotomy performed], subjects with successful implantation of the Scaffold [All Treated Set], subjects who completed the 12-month post-implantation visit, subjects who completed the 24-month post-implantation visit, subject in the Primary Endpoint Analysis Set, and subjects who withdrew early from the study and reason for discontinuation).

6.1.2 Protocol Deviations

A protocol deviation is any change, divergence, or departure from the study design or procedure defined in the protocol.

The following categories will be used to group protocol deviations:

1. Eligibility Not Met
2. Study Assessment Noncompliance
3. Other

The following are categorical reasons used to document why a protocol deviation occurred:

1. Subject Illness
2. Clinical Error
3. Investigator/Staff Decision
4. Other

A subset of the protocol deviations can be identified as a major protocol deviation as described below:

Major Protocol Deviation: A major protocol deviation that may significantly affect the completeness, accuracy, and/or reliability of the study data or that might significantly affect a subject's rights, safety, or well-being.

To determine inclusion in the Primary Endpoint Analysis set, major protocol deviations will be categorized into the following subgroups:

- Major Data Protocol Deviations - protocol deviations related to the completeness, accuracy, and/or reliability of the study data.
- Major Good Clinical Practice (GCP) Protocol Deviation - protocol deviations related to subject's rights, safety, or well-being but do not affect the completeness, accuracy, and/or reliability of the study data.

Subjects with Major Data Protocol Deviations that occurred in the time period through the 6 Month Primary Endpoint Visit will be excluded from the Primary Endpoint Analysis Set.

Subjects with only no protocol deviations or subjects with minor and/or Major GCP Protocol Deviations will not be excluded from the Primary Endpoint Analysis Set.

All documented protocol deviations in the study will be reviewed on an ongoing basis to identify all Major Protocol Deviations by a data review team including representatives from clinical operations, medical, data management, and statistics, and sent to the sponsor for approval. Final decisions will be documented and archived.

Number and proportion of subjects with protocol deviations (major/all other deviations) may also be tabulated by protocol deviation category if data warrants. Subjects excluded from each analysis set will be tabulated.

6.1.3 Demographics

A demographic and baseline characteristics table will be presented for the Safety Set. The summary will include descriptive statistics for age, sex, race, ethnicity, weight, height, BMI at baseline, as well as the cause of spinal cord injury. Skeletal maturity will be summarized through Risser Staging for subjects aged 16 and 17 if applicable.

6.1.4 Medical and Surgical History

At the Screening visit, the general medical and surgical procedures history will be recorded on the eCRF, Medical/Surgical History data will be listed.

6.1.5 Concomitant Medications, Interventions, and Procedures

Prior and concomitant medications will be coded to the therapeutic drug classes and generic drug names using the World Health Organization Drug (WHODrug) classifications version March 2014 [8]. All prior and concomitant medications, interventions and procedures will be tabulated by Anatomical-Therapeutic-Chemical (ATC) Level 3 Code and Preferred Term.

Concomitant interventions and procedures will be listed by subject.

6.2 Efficacy Analysis

The primary analysis of the study will be presented upon completion of the 6 Month Primary Endpoint Follow-up Visit (6 Months post-Scaffold) for the subjects in the Primary Endpoint Analysis Set. For the purposes of the Primary Endpoint Analysis, the Primary Efficacy Endpoint Analysis will be performed on the Primary Endpoint Analysis set. All secondary, exploratory, and other efficacy analyses will be performed on the All Treated Set.

Additional efficacy and subgroup analyses may be performed for information obtained after the 6 Month Primary Endpoint Follow-up Visit (12 month and 24 month post-Scaffold follow-up visits), as needed.

6.2.1 Primary Endpoint Analysis

The Primary Endpoint Analysis will be performed when the 16th subject in the Primary Endpoint Analysis completes the 6-month post-implantation visit.

The primary endpoint analysis is the proportion of subjects from the Primary Endpoint Analysis Set who have an improvement of at least 1 grade on AIS assessment at the 6-month Primary Endpoint Follow-up Visit. The number and percent of subjects with an improvement of at least 1 grade on AIS assessment will be presented. If the proportion of subjects who demonstrate an improvement of at least 1 grade on AIS is at or above 25% the study will be deemed a success using this preset Objective Performance Criterion (OPC) of $\geq 25\%$ as a measure of success.

The primary endpoint analysis will also be conducted utilizing the All Treated Analysis Set. This analysis will be performed in the same manner as described above as a confirmatory analysis. In addition, a sensitivity analysis will be performed that will impute a value for any missing AIS grade at the 6-month Primary Endpoint Follow-up Visit. Any subject who does not have a 6-month Primary Endpoint Follow-up Visit for any reason including premature study withdrawal, will have the primary endpoint imputed to not having an improvement of at least 1 grade on AIS assessment at the 6-month Primary Endpoint Follow-up Visit unless they were assessed as AIS C or better at the last two study visits.

Additionally, the AIS grade will be tabulated by subject at each visit in the All-Treated Set. The number and percentage of subjects with each AIS grade will be tabulated at each visit.

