3.2.1 Sample Size Considerations

The study planned to enroll up to 36 subjects to ensure 20 subjects in the Primary Endpoint Analysis Set (Section 5.1). The sample size was determined for the purpose of the study without a formal statistical null hypothesis.

At the time of Primary Endpoint Analysis, it was determined to close enrollment with 16 subjects meeting the Primary Endpoint Analysis Set criteria.

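### The SAP gives incompatible data-cut rules for the primary analysis, and the 16th-subject rule could leave out implanted subjects who are not yet due at month 6

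*SAP*

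**What the plan says.** Five places in the SAP bear on when the primary analysis is done.

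- **5.3, database lock:** "The clinical database will be locked after all subjects complete their 6-month Primary Endpoint Follow-up Visits for the Primary Endpoint Analysis".
- **6, source of the outputs:** the shells are to match the tables, listings and figures "when they are created from the locked database". The lock therefore governs what is analysed.
- **5.4, primary analysis:** "At the time of the last subject in the Primary Endpoint Analysis set completes the 6 Month Post-Implantation Visit". **6.2** likewise refers to completion of the 6-month visit "for the subjects in the Primary Endpoint Analysis Set".
- **6.2.1, primary endpoint:** "The Primary Endpoint Analysis will be performed when the 16th subject in the Primary Endpoint Analysis completes the 6-month post-implantation visit".
- **6.3, primary safety analysis:** presented on completion of the 6-month visit "for the subjects in the Safety Set Excluding Screen Failures".

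Under 5.1, the Primary Endpoint Analysis Set requires a successful implant, no major deviation affecting data quality and a completed 6-month visit. The All Treated Analysis Set requires only the successful implant. Section 3.2.1 adds that "it was determined to close enrollment with 16 subjects meeting the Primary Endpoint Analysis Set criteria", without giving the number implanted or the number still in follow-up.

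Section 6.2.1 declares success if the observed proportion is 25% or more. Its sensitivity analysis scores anyone without a 6-month visit, whatever the reason, as not improved, unless the subject was AIS C or better at the last two visits.

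**The concern.** All subjects reaching month 6 and the 16th Primary-Set subject reaching month 6 are different events, because the Primary Endpoint Analysis Set is only part of the implanted population. Section 2 lets the SAP override the protocol's statistical section, so the SAP itself should settle which event counts.

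The choice matters only if an implanted subject has not reached month 6 when the 16th qualifying subject does. Under 6.2.1 that subject cannot be in the primary set. In the All Treated analysis the subject has no 6-month grade. In the sensitivity analysis the subject normally counts as a failure, although the outcome is not missing but simply not due. Under a literal reading of 5.3 the same subject would be observed first and, if qualifying, would enter the primary denominator.

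Success is a point-estimate threshold with no formal test (5.2), so one subject more or less in the denominator can decide the study's declared result.

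**Working it through.** **Text check.** The rules compare as follows.

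| SAP section | What is timed | Whose 6-month visits |
|---|---|---|
| 5.3, with 6 | database lock, hence outputs | all subjects |
| 5.4 | primary analysis and study report | last subject in the Primary Endpoint Analysis Set |
| 6.2 | primary analysis | Primary Endpoint Analysis Set |
| 6.2.1 | primary endpoint analysis | 16th subject in that set |
| 6.3 | primary safety analysis | Safety Set Excluding Screen Failures |

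Sections 5.4, 6.2 and 6.2.1 agree with each other if 16 is the final size of the set. Sections 5.3 and 6.3 do not agree with them as worded.

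**Inputs for the consequence.** The success threshold is 25% (6.2.1), the cut is at n = 16 (6.2.1), and the spontaneous improvement rate is 13% to 16% (3.2). The 16 has no formula, alpha or power behind it (3.2.1, 5.2), so there is no plan figure to reproduce. The number pending, k, is not in the SAP. I assume k = 1 to 4 and that every pending subject eventually qualifies for the primary set.

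**Responders needed.** The minimum is 0.25n rounded up: 0.25 × 16 = 4, and 0.25 × 17 = 4.25, so 5. It stays at 5 up to n = 20 (0.25 × 20 = 5).

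**Exactly four responders.** If no pending subject improves: 4/16 = 25.0% (success), 4/17 = 23.5%, 4/18 = 22.2%, 4/19 = 21.1%, 4/20 = 20.0% (all failures).

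**Chance of meeting the rule**, exact binomial P(X ≥ minimum):

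| n | minimum | true rate 13% | true rate 16% |
|---|---|---|---|
| 16 | 4 | 14.5% | 24.6% |
| 17 | 5 | 6.0% | 12.2% |
| 18 | 5 | 7.4% | 14.8% |
| 19 | 5 | 9.0% | 17.6% |
| 20 | 5 | 10.8% | 20.6% |

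At these rates, 16 is the easiest of the five sizes to pass.

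**Chance that the result changes.** With k = 1, success becomes failure only if exactly 4 of 16 improve and the 17th does not. The joint probability is C(16,4) p⁴ (1−p)¹² × (1−p):

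- p = 0.13: 1820 × 0.13⁴ × 0.87¹³ = 8.5%
- p = 0.16: 1820 × 0.16⁴ × 0.84¹³ = 12.4%

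These equal the drop in passing probability from n = 16 to n = 17 (14.48% − 5.98% and 24.60% − 12.24%), because the reverse change is impossible with k = 1. For larger k, the joint probabilities over all outcomes are:

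| k | success to failure, 13% / 16% | failure to success, 13% / 16% |
|---|---|---|
| 1 | 8.5% / 12.4% | 0% / 0% |
| 2 | 7.4% / 10.4% | 0.3% / 0.6% |
| 3 | 6.4% / 8.7% | 1.0% / 1.7% |
| 4 | 5.6% / 7.3% | 1.9% / 3.3% |

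If k = 0, nothing changes.

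**The case against.** The strongest reply is that the SAP shows no pending subject. Section 3.2.1 reports, in the past tense, that enrollment closed with 16 subjects meeting criteria that include a completed 6-month visit. The others implanted may all have completed with a major data deviation, or withdrawn. A reader might infer that the 16th-subject rule does cut the data before other implanted subjects reach their endpoint. The document does not support that; it supports only that the rule could. This part of the objection stands.

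Second, 5.3 concerns the lock and 6.2.1 the analysis, and all subjects cannot complete month 6 if anyone withdraws earlier, as 6.2.1 expects. The phrase may therefore mean all subjects who count for the primary analysis. That is plausible and would remove the conflict with 6.2.1, but the text does not say it and 6.3 would still differ. If 5.3 is taken literally, the lock controls and nobody is cut off. The harm thus needs 6.2.1 to be followed over 5.3, and the SAP does not say which prevails.

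Third, a pending subject still appears in the by-subject AIS tabulation for the All Treated Set, and the failure imputation is confined to a labelled sensitivity analysis, where it works against the device. This is true and limits the damage, but it does not settle who belongs in the primary denominator.

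A reader might also tie this point to the open-label review of deviations in 6.1.2, with sponsor approval. That concern would exist under either trigger and does not bear on the conflict.

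**Conclusion.** The point holds as a conflict of wording with a conditional consequence. Sections 5.3 (with 6), 5.4, 6.2, 6.2.1 and 6.3 do not give one event for the data cut, and no rule reconciles them.

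If one implanted subject was pending and later qualified, the chance that a success at 16 would be a failure at 17 is 8.5% to 12.4% at true rates of 13% to 16%. With two to four pending it is 5.6% to 10.4%. A change from failure to success, such as 3/16 becoming 5/18, is possible but unlikely: with two pending the chance is 0.3% to 0.6%. These figures rest on an assumed number pending and on true rates equal to the SAP's spontaneous rates. If nobody was pending, the declared result is unaffected and only the wording needs repair. The SAP should be corrected because the change is cheap and the 25% rule can turn on one subject.

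**What to change.** Use one data-cut rule in 5.3, 5.4, 6.2, 6.2.1 and 6.3: lock and analyse once every implanted subject has completed the 6-month visit, passed the end of its +30-day window (Table 1) or left the study. In the same edit:

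- include everyone who qualifies for the Primary Endpoint Analysis Set, even beyond 16;
- state how many implanted subjects were pending when the 16th qualifying subject completed month 6;
- limit the failure imputation in 6.2.1 to subjects whose 6-month visit was due;
- clarify the lock sentence in 5.3, which as worded also makes the lock wait for the study report to be written.

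The cost is SAP wording and a possible wait. The cut comes at most about 7 months after the last implant (6 months plus 30 days), with no delay if nobody is pending.
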